CGM System Glucose Ranges (mg/dL)	Number of Paired CGM-YSI	Mean Relative Difference (%)	Median Relative Difference (%)	Mean Absolute Relative Difference (%)	Median Absolute Relative Difference (%)
Overall					
40-60*					
61-80*					
81-180					
181-300					
301-350					
351-400					

*For CGM ≤ 80 mg/dL, the differences in mg/dL are included instead of percent difference (%).

Table 6C. CGM System Agreement to Reference within YSI Glucose Ranges (Sample Table)

YSI Glucose Range (mg/dL)	Number of Paired Eversense™ CGM and YSI Reference	Percent of CGM System Readings Within				
		Percent 15/15% of Reference	Percent 20/20% of Reference	Percent 30/30% of Reference	Percent 40/40% of Reference	Percent Greater than 40/40% of Reference
Overall						
< 40						
40 - 60						
61 - 80						
81 - 180						
181 - 300						
301 - 350						
351 - 400						
> 400						

Table 6D. CGM System Agreement to Reference within CGM System Glucose Ranges (Sample Table)

CGM System Glucose Range (mg/dL)	Number of Paired Eversense™ CGM and YSI Reference	Percent of CGM System Readings Within				
		Percent 15/15% of Reference	Percent 20/20% of Reference	Percent 30/30% of Reference	Percent 40/40% of Reference	Percent Greater than 40/40% of Reference
Overall						
40 - 60						
61 - 80						
81 - 180						
181 - 300						
301 - 350						
351 - 400						

Table 7A. Concurrence of CGM System Readings and YSI Values within YSI Glucose Ranges (Sample Table)

YSI (mg/dL)	Number of Paired CGM-YSI (n)	Percent of Matched Pairs in Each CGM System Glucose Range for Each YSI Glucose Range									
		CGM (mg/dL)	40-60	61-80	81-120	121-160	161-200	201-250	251-300	301-350	351-400
<40											
40-60											
61-80											
81-120											
121-160											
161-200											
201-250											
251-300											
301-350											
351-400											
>400											

Table 7B. Concurrence of CGM System Readings and YSI Values within CGM System Ranges (Sample Table)

CGM (mg/dL)	Number of Paired CGM-YSI (n)	Percent of Matched Pairs in Each YSI Glucose Range for Each CGM Glucose Range YSI (mg/dL)										
		<40	40-60	61-80	81-120	121-160	161-200	201-250	251-300	301-350	351-400	>400
40-60												
61-80												
81-120												
121-160												
161-200												
201-250												

CGM (mg/dL)	Number of Paired CGM-YI (n)	Percent of Matched Pairs in Each YSI Glucose Range for Each CGM Glucose Range YSI (mg/dL)									
		<40	40-60	61-80	81-120	121- 160	161- 200	201- 250	251- 300	301- 350	351- 400
251-300											
301-350											
351-400											

Table 8. CGM System Accuracy by Visit Number (Sample Table)

Day Number	Number of Paired CGM-YI	Mean Absolute Relative Difference (%)	Median Absolute Relative Difference (%)	Percent of CGM System Readings Within				
				Percent 15/15% of Reference	Percent 20/20% of Reference	Percent 30/30% of Reference	Percent 40/40% of Reference	Percent Greater than 40/40% of Reference
Day 1								
Day 7								
Day 14								
Day 30								
Day 60								
Day 90								

Table 9. CGM System between System Precision (Sample Table)

Level of Mean Glucose (mg/dL)	Mean Difference (Sensor 1 - Sensor 2) (mg/dL)	SD of Difference (mg/dL)	N Pairs
<= 70			
71-180			
> 180			
All			
PARD			
PCV			

Table 10A. CGM System Performance during Sleep Challenges (Sample Table)

Night Time (Y/N)	Number of Paired CGM-YI	Mean Absolute Relative Difference (%)	Median Absolute Relative Difference (%)	Percent of CGM System Readings Within				
				Percent 15/15% of Reference	Percent 20/20% of Reference	Percent 30/30% of Reference	Percent 40/40% of Reference	Percent Greater than 40/40% of Reference
Y								
N								

Table 10B. CGM System between System Precision during Sleep Challenges (Sample Table)

Night Time (Y/N)	N Pairs	PARD
Y		
N

1 OVERVIEW

This document outlines the statistical analysis plan (SAP) for the PRECISION evaluation study. It is intended to outline the statistical procedures and methods used to design the study and to analyze the resulting clinical data, in conformance with the recommended practices contained in *ICH E9 Statistical Principles for Clinical Trials*. The statistical procedures that are described in this document are consistent with those contained in the associated *Protocol Number CTP-0031* but contain additional details on their implementation. Senseonics data processing procedure will follow PLN-0079.

Changes to the original released version of this SAP will be documented in its document history. Deviations from the applicable SAP version will be documented and described in any reporting of study statistical results.

2 DEVICE OVERVIEW

The **Senseonics Continuous Glucose Monitoring (CGM) System** is a glucose monitoring device indicated for continually measuring interstitial fluid glucose levels in adults with diabetes for the operating life of the Sensor. The Senseonics Continuous Glucose Monitoring System is intended to be used:

- To provide real-time glucose readings directly to the user.
- To provide glucose trend information.
- To provide alerts for the detection and prediction of episodes of low blood glucose (hypoglycemia) and high blood glucose (hyperglycemia).

3 STUDY DESIGN

This is a non-randomized, prospective, single-arm, multi-center study, whereby approximately 44 subjects will be enrolled and 36 subjects will be inserted in the United States at up to 4 sites. The investigation will include both clinic visits and home use of the Senseonics CGM System. The subjects will have one or two Sensors inserted by trained Investigators. The Sensors will be inserted in the upper arms of the subjects. The accuracy of the Senseonics CGM System will be evaluated during clinic visits comparing Sensor glucose values and plasma glucose values measured on a bedside glucose analyzer. For qualifying subjects, during the clinic visits, there will be planned hyperglycemia and hypoglycemia challenges. Effects of compression/sensor dropout will be evaluated during the designated overnight periods.

In this study, including the clinic and home settings, all diabetes care decisions will be based on SMBG blood glucose values and clinical standard of care, rather than Senseonics CGM System results.

This study will not be randomized. Subjects will be selected consecutively (i.e., selecting every subject in the order they present at the site) among those who meet the

inclusion/exclusion criteria.

The Subject visit schedule includes 9 visits over a period of approximately 4.5 months (inclusive of visit windows from screening visit through follow-up visit). A subset of a minimum of 6 and a maximum of 9 subjects will have blood samples drawn daily for the first 7 days of sensor wear for additional dexamethasone screening and to determine blood draw time points during the first week of sensor wear for the remaining subjects. These subjects will only have one sensor inserted in the left arm, which will be linked to the Gen 1 transmitter. Remaining subjects will have 2 sensors inserted, one in each arm, with the left sensor linked to a Gen 1 transmitter, and the right sensor linked to the Gen 2 transmitter. These subjects may be required to make additional visits for dexamethasone screening between visits 3 and 4.

The study is anticipated to take approximately 6 months, including the enrollment period.

4.1 Study Objectives

4.1.1 Effectiveness

The effectiveness objective is to determine the accuracy of the Senseonics CGM System through 90 days post-insertion for reference glucose values from 40-400 mg/dL. The exploratory objectives are to determine other relevant Senseonics CGM System performance measures during the period of Sensor use and are detailed further in Section 6, along with plans and analysis details on the effectiveness endpoint. An interim analysis will be performed and data submission will be made based on the sensor performance data accrued through the day 30 visit (Visit 6).

4.1.2 Safety

The safety objective is to demonstrate safety of the Senseonics CGM System through 90 days post-insertion by measuring the incidence of device-related or sensor insertion/removal procedure-related serious adverse events (SAEs) during the investigation. The other safety objectives are to evaluate the incidence of all procedure-related or device-related adverse events (AEs) in clinic and home use, and to evaluate the incidence of all adverse events, regardless of relatedness, in clinic and home use. The safety endpoints and their respective analysis are detailed further in Section 6.

4.2 Endpoints

4.2.1 Effectiveness Endpoint

The effectiveness objective is to descriptively document the distribution of absolute relative difference across all subjects and to estimate the MARD. The MARD will be estimated initially when all the subjects complete 30 days of Sensor use for the interim analysis, followed by the MARD based on all the follow-up data through 90 days of Sensor use.

The effectiveness endpoint will be calculated for three different combinations of 2 generations of hardware and 2 generations of firmware. The three configurations are Generation 1 (Gen 1)

transmitter plus study firmware, Generation 2 (Gen 2) transmitter plus study firmware and Gen 2 transmitter plus updated firmware.

Descriptive statistics will be provided for the MARD and other exploratory effectiveness endpoints. There is no hypothesis to be tested. No inferential statistical analysis will be performed.

The effectiveness endpoint is the mean absolute relative difference (MARD), defined as the average of absolute difference of paired Senseonics CGM System and reference glucose readings divided by the reference glucose reading (reference) for all reference glucose values, that is:

$$\text{MARD} = \left(\left(\sum \frac{|(\text{Glucose})_{\text{SENSOR}} - (\text{Glucose})_{\text{REFERENCE}}|}{(\text{Glucose})_{\text{REFERENCE}}} \right) / n \right) \times 100\%$$

Where, n is the total number of CGM and reference glucose pairs during the evaluation period, that is, after 30 days of Sensor use for the interim analysis, and after 90 days of use.

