	
10. Currently receiving (or likely to need during the study period): immunosuppressant therapy; chemotherapy; anticoagulant/antithrombotic therapy (excluding aspirin); glucocorticoids (excluding ophthalmic or nasal). This exclusion does include the use of inhaled glucocorticoids and the use of topical glucocorticoids (over sensor site only); antibiotic for chronic infection (e.g. osteomyelitis, endocarditis)
 
11. A condition requiring or likely to require magnetic resonance imaging (MRI)
 
12. Known topical or local anesthetic allergy
 
13. Known allergy to glucocorticoids
 
14. Any condition that in the investigator's opinion would make the subject unable to complete the study or would make it not in the subject's best interest to participate in the study. Conditions include but are not limited to psychiatric conditions, known current or recent alcohol abuse or drug abuse by subject history, a condition that may increase the risk of induced hypoglycemia or risk related to repeated blood testing. Investigator will supply rationale for exclusion
 
15. Participation in another clinical investigation (drug or device) within 2 weeks prior to screening or intent to participate during the study period
 
16. The presence of any other active implanted device (as defined further in protocol)
 
17. The presence of any other CGM sensor or transmitter located in upper arm (other location is acceptable)

Investigation Objectives	
Effectiveness Objective: To determine accuracy of the Senseonics CGM System measurements through approximately 90 days post-insertion. An interim analysis will be conducted on all subjects after completion of Visit 6 (day 30 accuracy visit).
 
Safety Objective: To demonstrate safety of the Senseonics CGM System through 90 days post-insertion or sensor removal and follow-up by measuring the incidence of device-related and insertion/removal procedure-related serious adverse events during the investigation.

Endpoints	
Effectiveness Endpoint: The effectiveness endpoint will be mean absolute relative difference (MARD) for paired Sensor and reference measurements through 90 days post-insertion for reference glucose values from 40-400 mg/dL. This endpoint will be evaluated descriptively. Neither inferential analysis nor hypothesis testing will be performed. An interim analysis will be conducted on all subjects after completion of Visit 6 (day 30 accuracy visit).

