6.3 Data for Analysis

All data will be used for the study safety and effectiveness analysis.

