6.9 Effectiveness Endpoint

Summary

The effectiveness endpoint will be the mean absolute relative difference (MARD), calculated for all paired Sensor and reference measurements through 90 days post-insertion. For the planned interim analysis, MARD will be based on the first 30 days post-insertion data.

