6.10.1.7 Effect of compression on sensor performance during sleep challenges

For the sleep assessment periods during visits 4 & 5, compression may occur to the sensor site when the subject is sleeping at night. The system's difference and agreement with reference and between system precision will be compared between the night time and the day time (Tables 10A and 10B in APPENDIX 1).

6.10.1.8 Mean Absolute Difference between sensor and reference measurements for reference values less than or equal to 80mg/dL

The mean absolute difference (MAD) for reference glucose values less than or equal to 80 mg/dL is defined as the absolute difference of paired Senseonics CGM System and Reference readings for reference glucose values ≤ 80 mg/dL.

$$MAD = \left(\sum |(Glucose)_{SENSOR} - (Glucose)_{REFERENCE}| \right) / n$$

This analysis will quantify both cumulative results as well as stability over time in 30 day intervals (Tables 11A and 11B in APPENDIX 1).

6.10.1.9 Mean Absolute Difference between sensor and reference measurements for system full scale range (40-400mg/dL)

$$MAD = \left(\sum |(Glucose)_{SENSOR} - (Glucose)_{REFERENCE}| \right) / n$$

This analysis will quantify both cumulative results as well as stability over time in 30 day intervals (Tables 11A and 11B in APPENDIX 1).

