YSI Glucose Ranges (mg/dL)	Number of Paired CGM-YSI	Mean Relative Difference (%)	Median Relative Difference (%)	Mean Absolute Relative Difference (%)	Median Absolute Relative Difference (%)
Overall					
<40*					
40-60*					
61-80*					
81-180					
181-300					
301-350					
351-400					
>400					

*For YSI ≤80 mg/dl, the differences in mg/dl are included instead of percent difference (%).

Table 6B. CGM System Difference to YSI within CGM System Glucose Range (Sample Table)

CGM System Glucose Ranges (mg/dL)	Number of Paired CGM-YSI	Mean Relative Difference (%)	Median Relative Difference (%)	Mean Absolute Relative Difference (%)	Median Absolute Relative Difference (%)
Overall					
40-60*					
61-80*					
81-180					
181-300					
301-350					
351-400					

*For CGM ≤ 80 mg/dL, the differences in mg/dL are included instead of percent difference (%).

Table 6C. CGM System Agreement to Reference within YSI Glucose Ranges (Sample Table)

YSI Glucose Range (mg/dL)	Number of Paired CGM and YSI Reference	Percent of CGM System Readings Within				
		Percent 15/15% of Reference	Percent 20/20% of Reference	Percent 30/30% of Reference	Percent 40/40% of Reference	Percent Greater than 40/40% of Reference
Overall						
< 40						
40 - 60						
61 - 80						
81 - 180						
181 - 300						
301 - 350						

YSI Glucose Range (mg/dL)	Number of Paired CGM and YSI Reference	Percent of CGM System Readings Within				
		Percent 15/15% of Reference	Percent 20/20% of Reference	Percent 30/30% of Reference	Percent 40/40% of Reference	Percent Greater than 40/40% of Reference
351 - 400						
> 400						

Table 6D. CGM System Agreement to Reference within CGM System Glucose Ranges (Sample Table)

CGM System Glucose Range (mg/dL)	Number of Paired CGM and YSI Reference	Percent of CGM System Readings Within				
		Percent 15/15% of Reference	Percent 20/20% of Reference	Percent 30/30% of Reference	Percent 40/40% of Reference	Percent Greater than 40/40% of Reference
Overall						
40 - 60						
61 - 80						
81 - 180						
181 - 300						
301 - 350						
351 - 400						

Table 6E. CGM System Difference to YSI within Glycemic Ranges (Sample Table)

YSI Glucose Ranges (mg/dL)	Number of Paired CGM-YSI	Mean Absolute Difference (mg/dL)	Mean Absolute Relative Difference (%)
Overall			
<70			
70-180			
>180			

Table 6F. CGM System Agreement to Reference within Glycemic Ranges (Sample Table)

YSI Glucose Range (mg/dL)	Number of Paired CGM and YSI Reference	Percent of CGM System Readings Within				

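### The MARD endpoint is limited to reference glucose 40-400 mg/dL in the synopsis and objectives, but computed over all reference values in its operative definition

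*SAP*

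**What the plan says.** **Limited to 40-400 mg/dL.** The Endpoints entry of the protocol synopsis defines the MARD for "paired Sensor and reference measurements through 90 days post-insertion for reference glucose values from 40-400 mg/dL". The effectiveness objective carries the same limit in Protocol 2.1 and in SAP 4.1.1 ("through 90 days post-insertion for reference glucose values from 40-400 mg/dL"). The expected-pairs table in Protocol 11.1.4 also has bins only from 40 to 400 mg/dL.

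**No limit.** Protocol 11.3.2.1, SAP 4.2.1 and SAP 6.9.1.1 give the formula and apply it "for all reference glucose values", with n as the total number of CGM-reference pairs. SAP 6.9 says the MARD is "calculated for all paired Sensor and reference measurements through 90 days post-insertion", and Protocol 11.3.1 says the same. SAP 6.3 adds: "All data will be used for the study safety and effectiveness analysis".

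**Table shells.** The SAP tables by YSI range (for example 6A and 6C in Appendix 1, 2.2 and 2.4 in Appendix 2) have rows for <40 and >400 next to an overall row. The tables by CGM value cover 40-400 only. The footnote to SAP Table 2.9 leaves out data when the system shows High or Low.

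**The concern.** The study has one effectiveness endpoint and no hypothesis, so the MARD point estimate is its result. SAP 4.2.1 has it calculated for three hardware/firmware configurations, and the day-30 version goes into a data submission before follow-up is complete. With two written definitions, two programmers can each follow the plan and report different values, and the range can be settled after the data are seen.

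The extra pairs are also not a neutral addition. The SAP describes 40-400 mg/dL as the system's full scale. If YSI is 35 mg/dL and the CGM correctly shows Low, no numeric pair forms. A pair forms only if the CGM shows 40 or more. Pairs outside the reference range are therefore selected on the direction of the sensor error.

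**Working it through.** **1. The plan's own figure.** Protocol 11.1.4 states 22,786 expected pairs, based on 66 sensors.
- Sensors: 6 × 1 + 30 × 2 = 66.
- Sum of the bin totals: 22,787.
- From the session columns: 3 × (4,632 + 2,965) = 22,791.

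The differences are rounding, so the figure reproduces. It counts no pair with a reference below 40 or above 400, so the planning matches the limited definition.

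**2. Formula for the shift.** Let f be the share of pairs with an out-of-range reference, M the in-range MARD and R the mean absolute relative difference (ARD) of the out-of-range pairs.

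MARD(all) = (1 − f) × M + f × R, so the shift = f × (R − M).

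The documents give none of f, M or R. All three are assumed below.

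**3. Size of the selection effect (assumed errors).** The sensor value is simulated given YSI, and only values within 40-400 are kept.

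| Reference range | Assumed error | Numeric readings | ARD before selection | ARD of retained pairs |
|---|---|---|---|---|
| YSI 30-39 | SD 10 mg/dL | about 30% | about 23% | about 33% (31-33% across runs) |
| YSI 401-440 | CV 10% | about 32% | about 8% | about 11% |

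Above 400, about 79% of the retained pairs are within 15% of reference, and their ARD is close to an in-range MARD of 10%. The distortion is mainly below 40 mg/dL.

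**4. Anchoring f to the plan (assumption: the decline between the last two bins continues at each end).**
- Below 40: 815 × (815 / 2,194) ≈ 303 comparisons. At 30% numeric, about 91 pairs.
- Above 400: 319 × (319 / 623) ≈ 163 comparisons. At 32% numeric, about 52 pairs.
- f = 143 / (22,786 + 143) ≈ 0.6%.
- Shift with M = 10%: [91 × (33 − 10) + 52 × (11 − 10)] / 22,929 = 2,145 / 22,929 ≈ 0.09 percentage points.

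**5. Wider assumptions.** M 9-12%, f 0.25-3%, R 10-60%.
- Lowest: 0.03 × (10 − 12) = −0.06 points.
- Highest: 0.03 × (60 − 9) ≈ +1.5 points.
- In between, with f = 1% (about 230 pairs), R = 40% and M = 10%: 0.01 × 30 = 0.30 points.

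The upper end is hard to square with Protocol 11.1.4. A share of 2.9% means about 680 extra pairs. At about 31% numeric, that needs about 2,200 out-of-range comparisons, while the two edge bins together expect 815 + 319 = 1,134 pairs.

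**The case against.** The strongest reply is that this is loose drafting. The objective sets the range, the synopsis repeats it in the endpoint, and "all" can be read as all values within it. That reading is possible, but no sentence states it. The SAP writes the range where it wants one: the heading of the exploratory mean absolute difference in 6.10.1.9 says "for system full scale range (40-400mg/dL". Even that measure is labelled as all results in Tables 11A and 11B. The rows for <40 and >400 show that out-of-range references are expected in the outputs.

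A second reply is that little depends on it: there is no hypothesis, no acceptance threshold, no power-based sample size and no stopping rule at the interim. This stands, and it limits the severity.

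A third reply is that the tables already separate <40 and >400, so a reader could recover either version. That does not work below 40. The table by YSI range carries the note "For YSI ≤80 mg/dl, the differences in mg/dl are included instead of percent difference", so the <40 row does not give the percent ARD needed to take those pairs out of the overall MARD.

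A fourth reply is that the all-data rule gives the unlimited version textual support too. It does, which is a reason to report that version as a sensitivity result. The range in the stated endpoint and objectives is the better choice for the headline.

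A reader might infer that only wrong readings can form an out-of-range pair, so that the added pairs are a worst case. The documents do not support that: CGM 40 against YSI 39, or 400 against 401, is an accurate pair. "Selected" is the right word.

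**Conclusion.** The inconsistency is real and unreconciled. It concerns what the headline number is, and it should be corrected. The likely effect is small: about 0.1 percentage point if the edge bins of the expected-pairs table are extrapolated (about 0.6% of pairs), with an assumed in-range MARD of 10% and the assumed sensor errors above. Under wider assumptions the shift runs from −0.06 to +1.5 points, but the documents give no out-of-range count, and nothing in them supports the upper part of that range.

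A reader might go further and infer that the choice of range could change the study's conclusion. The plan does not support that, since no test or threshold depends on the MARD. What is affected is the reproducibility of the reported estimate, including the one in the day-30 submission.

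**What to change.** - In Protocol 11.3.1 and 11.3.2.1 and in SAP 4.2.1, 6.9 and 6.9.1.1, define both the MARD and n for reference glucose values from 40-400 mg/dL, as the synopsis and objectives already do. Changing only the three formula sections would leave Protocol 11.3.1 and SAP 6.9 in conflict.
- Make the overall rows in Appendices 1 and 2 and the all-results level of SAP Tables 11A and 11B follow the same range.
- Keep <40 and >400 as separate descriptive rows.
- Report the MARD over all pairs as a descriptive sensitivity result.

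The cost is wording edits in several places and one extra descriptive figure. No new data are needed.
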